6.6.4. Clinically Relevant Disease

The proportion of participants with clinically relevant disease (See Section 6.4.1) by subcategory associated with RT-PCR-confirmed RSV-mediated ARI, LRTD and non LRTD will also be summarized per group, category and risk level for the first and second year separately and over the whole study. In case a participant had multiple RT-PCR confirmed RSV-mediated ARIs or LRTDs during the reported period, then the first occurrence of RT-PCR confirmed RSV-mediated ARI or LRTD will be used, respectively.

6.6.5. Vital Signs During the ARI episodes

The following will be summarized for the first and the second year separately and over the whole study.

Emerging vital sign abnormalities collected at ARI Day 3-5 for participants with an RT-PCR confirmed RSV-mediated ARI and/or LRTD will be summarized per vaccine group. An abnormality will be considered as emerging in a particular period if it is worse than the baseline value. The baseline value for efficacy will be used to define abnormalities (See Section 6.1.1). Please refer to Section 7.6 for the vital sign grades. If the baseline is missing, the abnormality is always considered emerging.

Moreover, for the determination of oxygen saturation collected by the vital signs page during the ARI Day 3-5, the number of subjects (and percentages) :

- with baseline $SpO_2 \geq 92\%$ and $SpO_2 < 92\%$ during the ARI episode,
- with baseline $SpO_2 < 92$ and that have a $\geq 3\%$ decrease during ARI episode
- and those with a missing baseline and $SpO_2 < 92\%$ during the ARI episode

will be tabulated per group, for participants with a RT-PCR confirmed RSV-mediated ARI and for those with a RT-PCR-confirmed RSV-mediated LRTDs.

In case a participant had multiple RT-PCR confirmed RSV-mediated ARIs or LRTDs during the reported period, then the first occurrence of RT-PCR confirmed RSV-mediated ARI or LRTD will be used, respectively.

6.6.6. RSV Viral Load.

The following will be summarized for the first and the second year separately and over the whole study.

For RSV A and RSV B viral load based on nasal swabs, descriptive statistics for ARI Day 1-2, ARI Day 3-5 and for the maximum viral load observed between the 2 visits, will be calculated for participants with a RT-PCR confirmed RSV-mediated ARI of the considered subtype and for those

with a RT-PCR-confirmed RSV-mediated LRTD of the considered subtype. The difference and 95% CI of the maximum log₁₀ viral load between the 2 groups will also be calculated. Means and standard errors will also be plotted.

For RSV A and RSV B viral load based on sputum will be listed.

In case a participant had multiple RT-PCR confirmed RSV-mediated ARIs or LRTDs during the reported period, then the first occurrence of RT-PCR confirmed RSV-mediated ARI or LRTD will be used, respectively.

For analysis purposes, for both nasal and sputum swabs, the qRT-PCR viral load will be imputed with the midpoint on the log scale between the limit of detection (LOD) and LLOQ of the RSV qRT-PCR assay when the result is ‘target detected’ (TD) but non-quantifiable.

1. For the RSV-A qRT-PCR assay, the LOD is 620 copies/mL and the LLOQ is 1000 copies/mL, a result that is TD will be imputed with 2.90 log₁₀ copies/mL.
2. For the RSV-B qRT-PCR assay, the LOD is 80 copies/mL and the LLOQ is 250 copies/mL, a result that is TD will be imputed with 2.15 log₁₀ copies/mL.

When the result is ‘target not detected’ (TND) (meaning below the LOD), for both RSV A and RSV B the value of TND will be imputed with the respective LODs.

RNA sequencing data, if available, will be explored with heatmaps.

6.6.7. Patient Reported outcomes

6.6.7.1. Respiratory Infection Intensity and Impact Questionnaire (RiiQ™v2)

The RiiQ consists of 4 scales that are scored separately. In the setting of the present study, only the RiiQ Symptom Scale (Question 1) and the RiiQ Impact on Daily Activities Scale (Question 2) will be used.

- **RiiQ Symptom Scale (Question 1).** Each symptom is rated on the following scale: 0=None, 1=Mild, 2=Moderate, and 3=Severe. Based on this questionnaire, the following will be calculated:
 - **RiiQ Total Symptom score** is the mean of all scores (based on 13 symptoms).
 - **RiiQ Lower Respiratory Symptom score** is the mean of the four lower respiratory scores (cough, short of breath, coughing up phlegm (sputum) and wheezing).
 - The **AUC (Section 7.9) for the change from baseline for the RiiQ Total Symptom score and the RiiQ Lower Respiratory Symptom score** during the ARI will be calculated.
- **RiiQ Impact Scale Question 2:**
 - **RiiQ Total Impact on Daily Activity score (Question 2)** consists of 7 activities. Ability to perform each activity item is rated on the following scale: 0=No difficulty, 1=Some difficulty, 2=Moderate Difficulty, and 3=Great difficulty. The total score is calculated as the mean of all 7 items (range 0-3).

- Moreover, the **AUC for the change from baseline for the RiiQ Total Impact on Daily Activity score** during the ARI will be calculated.

Note 1: Total scores will be calculated based on the number of assessments completed by the participant and in cases where more than 50% of the items needed to calculate the score is not collected, then the value for that score will be set to missing. For example, if a participant has responded to only 11 out of the 13 RiiQ symptom scale questions the ‘RiiQ Total Symptom score’ will be the mean of the 11 available questions. If the participant has only completed 6 or less of the questions, then the ‘RiiQ Total Symptom score’ will be set to missing.

6.6.7.1.1. Analysis Methods

RiiQ scores will be analyzed based on the PPE set, with a major focus on participants with RT-PCR-confirmed RSV-mediated ARI and LRTD, for the first, second year and the whole study. Part of the analysis might also be performed for participants with RT-PCR-confirmed hMPV-mediated and influenza-mediated ARI.

For the **total scores**, number of observations, mean, standard error, median, first and third quartile will be tabulated for the change from baseline for all RiiQ scores per group and means with standard errors may be graphically presented per group and time point for changes from baseline for different scores.

For the **total scores**, descriptive statistics at the start and end of each year as well as the change between the two timepoints will also be calculated for all participants based on the PPE set, for participants with RT-PCR-confirmed RSV ARI and those with RT-PCR-confirmed RSV LRTD, based on the PPE set.

For the **AUCs** number of observations, median, first and third quartile (q1, q3), minimum and maximum will be calculated and graphically presented with boxplots per group.

In case two or more assessments are reported at the same day then the worst total score will be used. The same applies for the AUC calculations. In case a participant had multiple RT-PCR confirmed RSV-mediated ARIs or LRTDs during the reported period, then the AUC corresponding to the first occurrence of RT-PCR confirmed RSV-mediated ARI or LRTD will be used, respectively.

6.6.7.2. Patient Global Impression Scores

- **Patient Global Impression of Health (PGI-H)**. Participants report their overall impression of their health status today on the following scale: 0=Very good, 1=Good, 2=Fair, 3=Poor, 4=Very poor
- **Patient Global Impression of Severity (PGI-S)**. Participants rate the severity of their respiratory illness on the following scale: 0=none 1=mild, 2=moderate, 3=severe.
- **Patient Global Impression of Change (PGI-C)**. Participants rate the amount of change in their health each day during an ARI episode on the following scale: -3= much better, -2=somewhat better, -1=A little better, 0=About the same, 1=A little worse, 2=somewhat worse, 3= much worse

The **AUC** (Section 7.9) **for the change from baseline for the PGI-H and the AUC of the actual values of the PGI-C and PGI-S** during the ARI will be calculated

- **Return to Usual Health.** Participants are being asked whether they have returned to their usual health after developing symptoms suggesting an ARI. The response is binary, yes/no.

Number of days a participant took to return to its usual health: This is counted based on the Return to Usual Health question.

- In case a participant indicated he returned to its usual health (based on the ‘Return to usual health’ question) on the last day he completed this questionnaire during the considered episode, this is calculated as: *the first day of a series where the participant answered consecutively ‘yes’ to the ‘Return to usual health question’ (with no intermittent ‘no’ answers) - the ARI start date based on the CRF+1* . For the Kaplan-Meier curve this is considered an event.
- In case a participant indicated he did not return to its usual health (based on the ‘Return to usual health’ question) on the last day he completed this questionnaire during the considered episode, this is calculated as: *the date of the last reply- the ARI start date based on the CRF + 1*. For the Kaplan-Meier curve this record will be censored.
- In case a participant never responded to any ‘Return to usual health’ question during an ARI episode then the number of days will be considered missing.

For example, if 2 participants completed the ‘Return to Usual Health’ question only for 8 days as indicated in Table 11. For participant 1 the number of days to return to usual health is 5 (15/11/2021- 11/11/2021+1) and this will be considered an event. For participant 2, the number of days to return to usual health is 8 (18/11/2021- 11/11/2021 + 1) and this record will be censored.

Table 11: Example for ‘Return to Usual Health’ question

	ARI Day 1 Onset (11/11/2021)	ARI Day 2 (12/11/2021)	ARI Day 3 (13/11/2021)	ARI Day 4 (14/11/2021)	ARI Day 5 (15/11/2021)	ARI Day 6 (16/11/2021)	ARI Day 7 (17/11/2021)	ARI Day 8 (18/11/2021)
Participant 1	No	No	Yes	No	Yes	Yes	Yes	Yes
Participant 2	No	No	Yes	Yes	Yes	No	No	No

Note: in case a participant has two or more different responses at the same day, then the ‘No’ answer will be taken into account for calculating the number of days a participant took to return to his usual health.

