- In the unlikely event where at least one nasal swab from an ARI episode cannot be tested at the site with the BioFire Filmarray Respiratory panel (eg, in the setting of instrument malfunction, unavailability of the device in the country/territory or at the site, or shortage of testing reagents at the site), this sample(s) should be sent to the central laboratory for testing with the BioFire Filmarray Respiratory panel, and the ARI episode will be followed up until ARI resolution (ie, with daily questionnaires and an ARI Day 29 visit) (refer to the procedures in the first bullet point below), independent of the results from other collected samples for that ARI episode. Further details on the strategy for local site and central testing of the nasal swabs and sputum samples are provided in Section 8.2.4.
- Participants with an ARI and a RT-PCR positive for RSV, hMPV, or influenza-mediated ARI will continue filling out the ARI episode questionnaires daily until resolution of the ARI episode (defined as 2 consecutive days with no symptoms listed on the RiiQ Symptom Scale, or, for participants who have RiiQ symptoms at baseline [assessed prevaccination], 2 consecutive days where all symptoms on the RiiQ Symptom Scale have returned to the same severity level as reported at baseline [or lower]). After resolution of the ARI episode, the participant will return to ARI surveillance with twice weekly reminders.

On ARI Day 29 (± 7 days), regardless of whether the ARI episode has resolved, participants with a RT-PCR positive for RSV, hMPV, or influenza-mediated ARI will be asked to return to the site. During this visit, the MRU questionnaire will be completed based on interview with the participant, participants will complete the RiiQ, the EQ-5D-5L and each of the Patient Global Impression (PGI) scales and the Return to Usual Health question, and the site staff will also collect information on days missed from work and on complications, hospitalizations and concomitant medications related to the ARI and record in the electronic case report form (eCRF). The ARI Day 29 visit can also take place by telephone or telemedicine contact.

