On ARI Day 29 (± 7 days), regardless of whether the ARI episode has resolved, participants with a RT-PCR positive for RSV, hMPV, or influenza-mediated ARI will be asked to return to the site. During this visit, the MRU questionnaire will be completed ([Appendix 11](#)) based on interview with the participant, participants will complete the RiiQ ([Appendix 8](#)), the EQ-5D-5L ([Appendix 9](#)) and each of the Patient Global Impression (PGI) scales and the Return to Usual Health question ([Appendix 10](#)), and the site staff will also collect information on days missed from work ([Appendix 12](#)) and on complications, hospitalizations and concomitant medications related to the ARI and record in the electronic case report form (eCRF). The ARI Day 29 visit can also take place by telephone or telemedicine contact.

For medically-attended RT-PCR positive for RSV, hMPV, or influenza-mediated ARIs, including those resulting in hospitalization, a standard question list will be provided ([Appendix 6](#)) to collect additional information on any other diagnostic tests (eg, chest x-rays, spirometry, pulmonary function tests, etc.) or on any interventions during the clinical course of the ARI.

Note: the same procedures apply for participants with a sputum sample taken and for participants with at least one nasal swab that cannot be tested at the site with the BioFire Filmarray Respiratory panel.

Participants will remain blinded as to the outcome of RSV, hMPV and influenza RT-PCR test results until study unblinding and the test results should only be disclosed in the event of safety concerns. RT-PCR test results related to the detection of other respiratory pathogens can be communicated to the participants. The RT-PCR results that are obtained with the BioFire Filmarray testing under the study procedures will be used for research purposes only and will not be used by the investigator for therapeutic decisions. A locally approved diagnostic test external to the study procedures, including the RSV RT-PCR, should be obtained in case the participant's own healthcare provider considers it warranted (eg, based on symptoms and/or risk of severe disease) and/or according to local/site specific guidelines. If a sample tests positive for SARS-CoV-2, the participant will be referred to their own healthcare provider for locally approved diagnostic test and further management, in accordance with local/site specific guidelines.

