Participants with positive RT-PCR results for RSV (or hMPV or influenza) should keep on filling out the daily ARI episode questionnaires until resolution of the ARI episode independently of any other co-infection (including SARS-CoV-2).

Further Procedures for Participants with an RSV, hMPV, or Influenza-mediated ARI^a

- Continue completing the RiiQ ([Appendix 8](#)) until resolution* of the ARI episode in the eDiary every evening (preferably).
- Continue completing the following scales until resolution* of the ARI episode:
 - EuroQoL, 5-Dimension, 5-Level (EQ-5D-5L) ([Appendix 9](#)),
 - Patient Global Impression of Health (PGI-H) scale,
 - Patient Global Impression of Severity (PGI-S) scale,
 - Patient Global Impression of Change (PGI-C) scale, and
 - Return to Usual Health question ([Appendix 10](#)).

* A resolved ARI episode is defined as 2 consecutive days with no symptoms listed on the RiiQ Symptom Scale, or, for participants who have RiiQ symptoms at baseline (assessed pre-vaccination), 2 consecutive days where all symptoms on the RiiQ Symptom Scale have returned to the same severity level as reported at baseline (or lower). After resolution of the ARI episode, the participant will return to ARI surveillance with twice weekly reminders.

- On ARI Day 29 (± 7 days), participants will be asked to return to the site if a sputum sample was provided by the participant at ARI Day 3-5 visit, regardless of the swab RT-PCR test results, AND/OR at least one of the nasal swab samples collected could not be tested at the study site with the BioFire Filmarray Respiratory panel (RT-PCR test) and had to be shipped for central laboratory test AND/OR at least one nasal swab sample had a positive RT-PCR result for either RSV, hMPV, or influenza when tested at the study site. The ARI Day 29 visit can take place by telephone or telemedicine contact. During this visit:
 - The MRU questionnaire will be completed ([Appendix 11](#)) based on interview with the participant.
 - Participants will complete the RiiQ ([Appendix 8](#)), the EQ-5D-5L ([Appendix 9](#)) and each of the PGI scales and the Return to Usual Health question ([Appendix 10](#)) on the participant's eDiary.
 - The site staff will also collect information on days missed from work ([Appendix 12](#)) and on complications, hospitalizations and concomitant medications related to the ARI and record in the eCRF.

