6.3.1. Definition of Endpoint

A participant will be considered to have RT-PCR-confirmed RSV-mediated LRTD if the following criteria are met:

- New onset or worsening from baseline of 3 or more of the below symptoms as captured in the RiiQ at the same assessment time point:
 - Cough
 - Short of breath
 - Coughing up phlegm (sputum)
 - Wheezing
- AND
- Confirmation of RSV by RT-PCR in one or more of the nasal swabs, or in the sputum sample (when available)

Prior to database lock for all planned analyses, the CEC will review all available data of all RT-PCR confirmed RSV-mediated ARIs and will confirm if the above criteria are met. If the CEC confirms that the criteria for RT-PCR-confirmed RSV-mediated LRTD are met, the cases will be counted as a primary endpoint in the statistical analysis. This will be done in two steps:

Step 1:

The set of RT-PCR confirmed RSV-mediated ARIs for which the CEC will review all available data will be determined programmatically as follows:

ARI episode definition

An ARI episode is defined as an episode reported by the participant and confirmed by the site, which is captured on the ‘Acute Respiratory Infection’ form of the CRF, meaning that all ARIs with a confirmed start (CESTDTC) and end (CEENDTC) date on this form will be considered an ARI episode. ARIs initiated by error and their respective symptoms will be removed from the analysis.

Note: In the cases that an RSV ARI is ongoing during the DB cut off, the database cutoff date will be used as an interim ARI end date for the purposes of the analysis. An ARI with no end date will be considered as an RSV ARI, if an RSV positive result is available within 15 days after the ARI onset.

ARI episode duration

The duration of an ARI episode is defined based on the ARI start and ARI end date reported in the CRF: *end date of ARI - start date of ARI + 1 (CEENDTC - CESTDTC + 1)*.

RSV RT-PCR Confirmation of the Considered ARI Episode

Confirmation of RSV infection by RT-PCR for the primary endpoint will be done in nasal swabs or sputum samples.

For samples collected outside of China, a sample is considered RSV positive if:

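### Time to return to usual health is censored at the last in-episode *No*, and the Day 29 answer to the same question has no stated role once the episode has closed

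*SAP*

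**What the plan says.** SAP 6.6.7.2 classifies each participant by the answer given "on the last day he completed this questionnaire during the considered episode". If that answer is *Yes*, the event day is the first day of the final unbroken run of *Yes*. If it is *No*, the time runs to that reply and "For the Kaplan-Meier curve this record will be censored". Protocol 9.4.1.4 and SAP 6.6.7.2.1 analyse the result with Kaplan-Meier curves and a Cox hazard ratio.

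The episode has its own window. SAP 6.3.1 bounds it by CRF dates, "meaning that all ARIs with a confirmed start (CESTDTC) and end (CEENDTC) date on this form will be considered an ARI episode", and adds: "The duration of an ARI episode is defined based on the ARI start and ARI end date reported in the CRF".

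Protocol 8.1 governs the daily questions in RSV, hMPV or influenza episodes: "Continue completing the following scales until resolution* of the ARI episode". The list that follows includes the Return to Usual Health question. Resolution is a symptom criterion: "A resolved ARI episode is defined as 2 consecutive days with no symptoms listed on the RiiQ Symptom Scale", or a return to baseline severity or lower for those with baseline symptoms. The site may also end an episode manually despite long-lasting symptoms above baseline.

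The question comes back at ARI Day 29 (±7 days). Protocol 4.1 says that, "regardless of whether the ARI episode has resolved, participants with a RT-PCR positive for RSV, hMPV, or influenza-mediated ARI will be asked to return", and the Synopsis says that at this visit "participants will complete the RiiQ, the EQ-5D-5L and each of the Patient Global Impression (PGI) scales and the Return to Usual Health question".

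**The concern.** The diary stops on a symptom criterion, while the endpoint is a different question. A participant can be free of RiiQ symptoms for two days and still answer *No*. That person leaves the risk set on the day the diary stops, although a later answer to the same question may be on file.

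Kaplan-Meier and Cox analyses assume that people censored on a given day have the same future recovery as those still followed. Here the usual trigger is symptom resolution, so those censored may well be closer to recovery than those who stay in the diary. SAP 6.6.1 shows the contrast. For ARI duration, reaching resolution is the event, and only episodes stopped early by the investigator are censored. For return to usual health, the same day becomes a censoring time. If the vaccine shortens illness, censoring times would also differ between arms.

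At stake is the recovery curve, and possibly the hazard ratio, for one exploratory endpoint. No confirmatory conclusion depends on it.

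**Working it through.** **1. Reproduce the plan's own example (SAP Table 11).** Day = date − ARI start date + 1, with ARI start 11/11/2021.
- Participant 1: the final run of *Yes* starts on 15/11, so 15 − 11 + 1 = 5 days, event.
- Participant 2: the last reply, on 18/11, is *No*, so 18 − 11 + 1 = 8 days, censored.

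Both match the SAP.

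**2. Add a Day 29 answer to the example (assumed).** Suppose participant 2's episode closed on Day 8 and the Day 29 answer is *Yes*. The SAP rule still gives 8 days, censored. The data say that recovery fell after Day 8 and by Day 29, an interval of 29 − 8 = 21 days. With the visit window (Day 22 to Day 36) the width is 14 to 28 days. Participant 1 is unchanged.

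**3. Who is affected.** The analysis is restricted to RSV-positive episodes, all of which are scheduled for the Day 29 contact. If the episode is still open then, Protocol 8.1 keeps the daily questions running and the Day 29 answer is in-episode. Only episodes closed before that contact, with a last answer of *No*, are affected.

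**4. Size, one-group illustration.** The documents give no inputs, so all of these are assumed (200,000 simulated episodes per scenario):
- symptom duration log-normal with median 10, 14 or 18 days and log-scale SD 0.5, the diary ending the day after;
- 10%, 30% or 50% still answering *No* at diary stop, who recover after a further exponential lag with mean 3 or 7 days;
- everyone else first answers *Yes* 0–3 days before the diary ends.

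Estimator: S(t) = ∏(1 − d_u/n_u) over days u ≤ t, under the SAP rule, compared with the true times.

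| Share still *No* | Recovery by Day 29, points too low | Median, days too long |
|---|---|---|
| 10% | 0–3 | 0 |
| 30% | 2–10 | 0–2 |
| 50% | 10–22 | 1–6 |

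Example: median duration 14 days, 30% late, lag 3 days gives true recovery by Day 29 of 91% against 82% under the rule, 9 points low, with median 16 against 17. Across all scenarios, about 59–96% of those censored would have recovered by Day 29.

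**5. Size, two-arm illustration (also assumed).** Symptom duration is 2 days plus a Gamma variable with shape 2, overall mean 16 days (placebo) and 12 days (vaccine). The lag is exponential with mean 6 days and the late share is the same in both arms. With 40% late in the placebo arm:

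| | True | SAP rule | Interval-censored with Day 29 |
|---|---|---|---|
| Recovered by Day 29 | 84% | 74% | 84% |
| Median (days) | 17 | 19 | 18 |

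Interval censoring restores recovery by Day 29 but moves the median little, because the intervals are wide. In the same model the hazard ratio under the rule, against the true times, is 1.59 against 1.56 (10% late), 1.57 against 1.52 (20%) and 1.59 against 1.48 (40%). These figures depend on equal late shares and lags in the two arms, which the documents neither state nor exclude.

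**The case against.** **The SAP does not expressly exclude Day 29.** A reader might infer that known recoveries are discarded by design. The text does not go that far. Where the SAP wants a strict start-to-end window it says so (symptom counting in 6.3.1, the AUC in 6.4.2), and 6.6.7.2 has no such sentence. The protocol also describes the Day 29 visit as part of following up certain episodes. This softens the point but does not remove it. On that reading, a *Yes* on Day 29 after a last daily *No* would be dated at about Day 29, which is too late. Either way, a rule for this answer is missing. Time up to the last *No* is kept in both readings.

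**The affected share may be small.** The RiiQ Symptom Scale has 13 items, including fatigue, interrupted sleep and loss of appetite, so resolution already covers much general malaise. This stands: no document supports any particular share, and at 10% the median does not move.

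**Not everyone censored is about to recover.** A reader might infer that they are. Episodes closed manually despite continuing symptoms are the counter-example. That censoring is also unlikely to be neutral, but it pulls the other way.

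**The hazard ratio.** A reader might infer a bias in a known direction. The illustration shows a modest shift under one set of assumptions. The share still answering *No*, and the lag, could differ by arm, so the documents do not fix the direction.

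**Little practical consequence.** The endpoint is exploratory, and SAP 6.11 does not list it among the efficacy endpoints kept after the study was terminated. This stands and limits the point to any other analysis that reports it.

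**Conclusion.** The point holds in limited form. For episodes closed before the Day 29 visit, the stated rule censors at the last in-episode *No* and gives no role to a later answer that the protocol collects. The censoring is plausibly informative, because it is triggered by symptom resolution or by site closure.

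Under assumed late shares of 10–40%, recovery by Day 29 is understated by about 0–10 percentage points and the median overstated by 0–2 days. These sizes rest entirely on assumed durations, shares and lags. The facts about the rule, the diary stop and the repeated question come from the documents. Materiality is low: one exploratory endpoint, with no effect on any confirmatory test.

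**What to change.** In SAP 6.6.7.2, state how the ARI Day 29 answer is used wherever this endpoint is reported:
- last in-episode answer *No*, Day 29 *Yes*: recovery is interval-censored between the two actual dates;
- last in-episode answer *No*, Day 29 also *No*: censor at the Day 29 visit date;
- Day 29 answer missing: keep censoring at the last reply;
- last in-episode answer *Yes*: unchanged.

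Fit an interval-censored curve and proportional-hazards model, either as the main analysis or as a prespecified sensitivity analysis beside the current Kaplan-Meier and Cox analysis. Do not impute the midpoint. In the two-arm illustration with 40% late, it gave medians of 19 days (placebo, true 17, current rule 19) and 17 days (vaccine, true 13, current rule 15), so it did not improve the medians.

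The cost is a few lines of SAP text and one extra standard procedure, with no new data collection. The drawback is wide intervals, about three weeks for an episode that closes around Day 8, so the gain is mainly in the estimate of recovery by Day 29 and only slightly in the median.
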